15.2 Headache Impact Test (HIT-6)

The HIT-6 (v1.0)⁴ is a Likert-type, self-reporting questionnaire designed to assess the impact of an occurring headache and its effect on the ability to function normally in daily life. The HIT-6 contains 6 questions, each item is rated from “never” to “always” with the following response scores: never = 6, rarely = 8, sometimes = 10, very often = 11, and always = 13. The total score for the HIT-6 is the sum of each response score and ranges from 36 to 78. The life impact derived from the total score is described as followed: Severe (≥ 60), Substantial (56-59), Some (50-55), Little to None (≤ 49).

15.3 Migraine Disability Assessment, Modified Version (mMIDAS)

The mMIDAS⁵ is a self-reporting questionnaire designed to assess absenteeism (complete disability) and presenteeism (reduced participation) in several domains, including work, school, family, social, and leisure activities. The total number of days with disability is rated on a 4-point scale, from the lower total score that indicates a Little or No Disability (0-5 days); Mild Disability (6-10 days); Moderate Disability (11-20 days) to the higher total score that indicates a Severe Disability (21 and more days). As the 20007A trial use the mMIDAS with a 1-month recall period, whereas the reference number of days provided in this paragraph is based on the original MIDAS version with a 3-months recall period, the disability levels in terms of number of days have to be adapted to a 1-month period. The following scoring will be used: Little or No Disability (0-1 days), Mild Disability (2-3 days), Moderate Disability (4-6 days) and Severe Disability (7 days or more). Both the mMIDAS scores and the mMIDAS scores multiplied by 3 will be presented.

15.4 Patient Global Impression of Change (PGIC)

The PGIC is a single patient-reported item reflecting the participant’s impression of change in their disease status since the Baseline visit (that is, in relation to activity limitations, symptoms, emotions, and overall quality of life).

The item is rated on a 7-point scale, where a low score indicate improvement (very much improved; much improved; minimally improved; no change; minimally worse; much worse; very much worse).

15.5 Most Bothersome Symptom (MBS)

The Investigator will verbally obtain the most bothersome symptom associated with the participant's migraines during the Screening Visit. Participants will be asked to rate the improvement in this symptom from screening on a 7-point scale identical to the scale used for the PGIC, i.e. the scale ranges from 1 (very much improved) to 7 (very much worse).

The MBS areas include: nausea, vomiting, sensitivity to light, sensitivity to sound, mental cloudiness, fatigue, pain with activity, mood changes, and other.

15.6 Migraine-Specific Quality of Life Questionnaire Version 2.1 (MSQ v2.1)

The MSQ v2.1⁶ is a participant-reported outcome designed to assess the quality of life in participants with migraine. It consists of 14 items covering three domains: role function restrictive (7 items); role function preventive (4 items); and emotional function (3 items). Each item is scored on a 6-point scale ranging from 1 (none of the time) to 6 (all of the time). Raw domain scores are summed and transformed to a 0 to 100 point scale. Higher scores indicate better quality of life.

The items going into each domain⁷ are specified in [Table 6](#).

Each item score is mapped from the recorded value of the item as shown in [Table 7](#).⁸

For each domain, the score is derived from the final item values by summing the scores from items within each domain and transforming the summed scores as shown in [Table 8](#).

Table 6 MSQ v.2.1 Domains

Domain	Item number	Abbreviated content
Role function restrictive	1 interfered with how well you dealt with family, friends, and others
	2 interfered with your leisure time activities such as reading or exercising
	3 had difficulty in performing work or daily activities
	4 kept you from getting as much done at work or at home
	5 limited your ability to concentrate on work or daily activities
	6 left you too tired to do work or daily activities
	7 limited the number of days you felt energetic
Role function preventive	8 cancelled work or daily activities . . .
	9 needed help in handling routine tasks
	10 stopped work or daily activities . . .
	11 not able to go to social activities . . .
Emotional function	12 felt fed up or frustrated
	13 felt like a burden on others
	14 afraid of letting others down

Table 7 MSQ v.2.1 Item Values

Response categories	Pre-coded item value	Final item value
None of the time	1	6
A little bit of the time	2	5
Some of the time	3	4
A good bit of the time	4	3
Most of the time	5	2
All of the time	6	1

Table 8 Derivation of MSQ v.2.1 Domain Scores

Domain	Sum of item scores range	Derivation
Role function restrictive	7 to 42	$(\text{Summed score} - 7) * 100/35$
Role function preventive	4 to 24	$(\text{Summed score} - 4) * 100/20$
Emotional function	3 to 18	$(\text{Summed score} - 3) * 100/15$

15.7 Hospital Anxiety and Depression Scale (HADS)

The HADS is a patient-rated scale designed to assess psychological distress in non-psychiatric participants. The HADS consists of two sub-scales: The D-scale measures depression and the A-scale measures anxiety. Each sub-scale contains 7 items, and each item is rated from 0 (absent) to 3 (maximum severity). The score of each sub-scale ranges from 0 to 21 and are analysed separately.

15.8 Euroqol 5 Dimension – 5 Levels (EQ-5D-5L)

The EQ-5D-5L⁹ is a patient-reported assessment designed to measure the participant's well-being. It consists of 5 descriptive items (mobility, self-care, usual activities, pain/discomfort, and depression/anxiety) and a visual analogue scale (VAS) of the overall health state. Each descriptive item is rated on a 5-point index ranging from 1 (no problems) to 5 (extreme problems) and a single summary index (from 0 to 1) can be calculated.

The VAS is scored separately and ranges from 0 (worst imaginable health state) to 100 (best imaginable health state).

15.9 Work Productivity and Activity Impairment: Migraine (WPAI:M)

The WPAI¹⁰ is a patient self-rated scale designed to provide a quantitative measure of the work productivity and activity impairment due to a specific health problem (WPAI:M). The WPAI assesses activities over the preceding 7 days and consists of 6 items: 3 items assess the number of hours worked, the number of hours missed from work due to the participant's condition, or due to other reasons, and 2 visual numerical scales to assess how much the participant's condition affects their productivity at work and their ability to complete normal daily activities.

The derivation of the WPAI:M sub-scores¹¹ is given in [Table 9](#), where Q1-Q6 refers to question 1-6 in the questionnaire. If both Q2 and Q4 has a score of 0 then both the Absenteeism and the Work productivity loss sub-scores are set to missing.

Table 9 Derivation of WPAI:M sub-scores

Sub-score	Description	Derivation
Absenteeism	Percent work time missed due to migraine	$100 * Q2 / (Q2 + Q4)$
Presenteeism	Percent impairment while working due to migraine	$100 * Q5 / 10$
Work productivity loss	Percent overall work impairment due to migraine	$100 * \left(\frac{Q2}{Q2 + Q4} + \left(1 - \frac{Q2}{Q2 + Q4} \right) * \frac{Q5}{10} \right)$
Activity impairment	Percent activity impairment due to migraine	$100 * Q6 / 10$

15.10 Treatment Satisfaction Questionnaire for Medicine – 9 Items (TSQM-9)

The TSQM-9¹² is a generic questionnaire assessing the participant's satisfaction with the medication. The tool consists of 9 items addressing effectiveness, convenience, and overall satisfaction of the IMP with 7-point scale for each item from 1- Extremely Dissatisfied to 7 - Extremely Satisfied. The TSQM-9 domain scores range from 0 to 100 with higher scores representing higher satisfaction on that domain. See [Table 10](#) for derivation.

Table 10 Derivation of TSQM-9 Domain Scores

Domain	Derivation
Effectiveness score	$[(Q1 + Q2 + Q3) - 3] / 18 * 100$
Convenience score	$[(Q9 + Q10 + Q11) - 3] / 18 * 100$
Overall satisfaction score	$[(Q12 + Q13 + Q14) - 3] / 14 * 100$

15.11 Health Care Resource Utilization (HCRU)

Migraine-specific healthcare resource utilization information will be collected in terms of outpatient health care professional visits (number of visits to doctor/general practitioner and number of visits to a specialist), number of emergency room visits, number of hospital admissions, as well as number of overnight hospitals stays during the past 4 weeks.

The items from the questionnaire will be analysed separately.

15.12 Severity of Dependence Scale Adapted for Headache (SDS:H)

The SDS:H is a patient reported scale, designed to assess dependency-like behaviour in participants with headache. The SDS:H is performed as a semi-structured interview, where the following questions will be addressed: 1) Do you think your use of headache medication was out of control? 2) Did the prospect of missing a dose make you anxious or worried? 3) Did you worry about your use of your headache medication? 4) Did you wish you could stop? 5) How difficult would you find it to stop or go without your headache medication? Each item is scored on a 4-point scale ranging from 0 (never/almost never, question 1-4, and not difficult, question 5) to 3 (always/nearly always, question 1-4, and impossible, question 5).

15.13 Assigning Data to Visits

See Section 3.1 for definition of Baseline.

15.13.1 BI and SDS:H

With respect to the Brief Educational Intervention (BI), data will be assigned to visits, regardless of the timing of the BI, also in the case the BI was missed. If an observation for SDS:H exist with visit label equal to Visit 2, it will be assigned to Visit 2, also in the case it was done after the Visit 2 date. Similarly, if an observation for SDS:H exist with visit label equal to Visit 5, it will be assigned to Visit 5, also in the case it was done after the Visit 5 date.

15.13.2 Pharmacoeconomic Assessments (ePROs)

For treated patients withdrawing prior to Week 12, the withdrawal visit will also include efficacy evaluations (PGIC, MBS, HADS, HIT-6, mMIDAS, MSQ, EQ-5D-5L, HCRU, WPAI:M and TSQM-9). These assessments will be assigned to nominal Visit 5.

Using the same principle for participants withdrawing in the open-label period after infusion of the IMP at Visit 5, the ePRO assessments will be assigned to nominal Visit 7.

Unscheduled visits will not contain assessments of the ePROs mentioned above.

ePROs will be summarized based on the following visit assignment rules to be applied for each ePRO endpoint separately:

- If exactly one observation exists for a specific visit label, this should be used.
- If more than one observation exist for a specific visit label the following would apply:
 - Week 4 (Visit 3): Choose the observation closest to Analysis day (ADAY) = 26.
 - Week 12 (IMP Visit 5): If one or more observations exist that are made prior to the IMP infusion at visit 5, choose the one closest to the IMP infusion at visit 5. If no such observation exists, choose the one closest to ADAY = 82.
 - Week 24 (Visit 7): Choose the observation closest to 82 days after the IMP Visit 5 date.
- Any remaining observations that are not assigned to a visit after this procedure, will constitute candidates for assignment to a trial visit using the assignment rules for withdrawals stated above. In case there is any observation on Visit 5/Visit 7 reflecting a planned assessment, this will take precedence over the candidate. In case, no planned assessments are present at Visit 5 or Visit 7 visits, the observation closest to ADAY = 82, or 82 days after IMP Visit 5, respectively, will be chosen. For an observation to be assigned to Visit 7, IMP needs to have been administered at Visit 5.

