The EoT Visit (Visit 7) will be performed at Week 24, 12 weeks after the administration of the second IMP infusion. A Safety Follow-up Contact (Visit 8) will be performed 8 weeks after the EoT Visit. Participants who withdraw from the study, except for those who withdraw their consent or are lost to follow-up, will be asked to attend a Withdrawal Visit as soon as possible and a subsequent Safety Follow-Up Visit 20 weeks after the last administration of IMP.

Participants who withdraw the informed consent should complete the safety follow-up and be withdrawn from the study.

Participants in the trial will have access to appropriate medical care in accordance with usual clinical practice after they complete or withdraw from the trial.

3 Definitions

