3.9.2 Definition of MOH during the trial

Panel 4 IHS ICHD-3 Guidelines for MOH

- A. Headache occurring on ≥ 15 days/month in a patient with a pre-existing headache disorder
- B. Regular overuse for >3 months of one or more drugs that can be taken for acute and/or symptomatic treatment of headache
- C. Not better accounted for by another ICHD-3 diagnosis

Regular overuse is defined either on:

- 10 days of use/month or more for >3 months of ergotamine, triptan, opioid (butorbital in US), or combination of analgesics
- 15 days of use/month or more for >3 months of non-opioid analgesics (paracetamol [acetaminophen], acetylsalicylic acid, NSAIDs)

In [Panel 4](#) above, the IHS ICHD-3 Guidelines for MOH are stated and used to confirm the MOH diagnosis at the screening visit.

During the trial, to evaluate whether a participant continues to overuse acute migraine medication, the eDiary data will be used for a specific post-baseline 4-week period (28-day period) only and the steps below will be followed:

Check acute migraine medication overuse in the reported month.

Count the number of days on which a medication was taken to treat a headache for each pre-defined acute migraine medication in the reported month (28-days period).

If the participant meets any of the following criteria in the reported month, the participant is considered as overusing acute migraine medication, used as “MOH” in the endpoint definitions. N is the number of monthly days.

- $N \geq 10$ days with either ergotamine, or $N \geq 10$ days with triptan
- $N \geq 10$ days with combination of two or more drug classes among ergotamine, triptan, opioid analgesic and non-opioid analgesics
- $N \geq 10$ days on which combination analgesics are taken.
- $N \geq 15$ days on which a non-opioid analgesic (paracetamol, acetylsalicylic acid, NSAIDs, analginum, antipyrine, tolfenamic acid) is taken. The overuse could be with a single non-opioid analgesic or with several of them.

4 Analysis Sets

The following analysis sets will be used to analyse and present the data:

- *all-participants-screened set (APSS)*
- *all-participants-randomized set (APRS)* – all randomized participants
- *all-participants-treated set (APTS)* – all participants in the APRS who received an infusion of the IMP in the Placebo-controlled Period
- *full-analysis set (FAS)* – all participants in the APTS who had a valid baseline assessment and at least one valid post-baseline 4-week assessment of MMDs in Weeks 1-12

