- Change from baseline to Weeks 13-24 in MHDs (Only descriptive summaries)
- Change from baseline to Weeks 13-24 in monthly days with acute migraine medication use (Only descriptive summaries)
- Change from baseline to Weeks 13-24 in monthly days with triptan or ergotamine medication use (Only descriptive summaries)
- Change from baseline to Weeks 13-24 in monthly days with individual non-opioid analgesics or NSAID medication use (Only descriptive summaries)

For the following endpoints based on response rates, treatment effects of EPTI compared to PBO will be analysed using logistic regression. The model will include baseline MMDs or MHDs as a continuous covariate, and treatment, country and previous treatment failures as factors. The logistic regression model will be fitted using the maximum likelihood (ML) method and the logit link function. For handling of missing MMD and MHD values, see Section 15.1.2. The odds ratios for EPTI compared to PBO will be estimated from the model and presented with p-values based on the likelihood ratio test and 95% CIs based on the profile likelihood. In case of convergence, sparsity or separation issues, refer to Section 15.15 for the pooling rule.

- Response: $\geq 50\%$ reduction from baseline in MMDs (Weeks 1-4, Weeks 1-12)
- Response: $\geq 75\%$ reduction from baseline in MMDs (Weeks 1-4, Weeks 1-12)
- Response: $\geq 50\%$ reduction from baseline in MHDs (Weeks 1-4, Weeks 1-12)
- Response: $\geq 75\%$ reduction from baseline in MHDs (Weeks 1-4, Weeks 1-12)

The following endpoints based on health-related quality of life scores test between EPTI and PBO at Week 4, Week 12 will use the similar MMRM model defined in the primary analysis. The baseline MMD score will be replaced with the baseline score for the corresponding endpoint in the model:

- Change from baseline to Week 4 and Week 12 in the HIT-6 total score
- Change from baseline to Week 4 and Week 12 in the mMIDAS total score
- Change from baseline to Week 4 and Week 12 in the MSQ v2.1 sub-scores (Role Function-Restrictive, Role Function-Preventive, Emotional Function)
- Change from baseline to Week 4 and Week 12 in the EQ-5D-5L VAS score
- Change from baseline to Week 12 in the WPAI:M sub-scores (Absenteeism, Presenteeism, Work productivity loss, Activity impairment)
- Change from baseline to Week 4 and Week 12 in HADS – depression, and anxiety subscale scores

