15.1.1 Monthly Migraine Days /Monthly Headache Days

The following describes the derivation of MMDs. The derivation of MHDs follows the same principles. Definitions of a migraine day and a headache day are described in Section 3.6.

Pooling of symptoms

To assess whether a headache is a migraine headache, daily reported symptoms will be pooled to assess the migraine criteria described in Section 3.6. The worst reported symptom will be used, for example, if different levels of worst pain have been reported on different days of the same headache, the worst of these levels will be used to assess the migraine criteria.

Regarding successful medication use for the criterion “a headache that is successfully treated with a triptan, ergotamine, or other migraine-specific acute medication”: a medication can only be considered successful if the question *“Did at least one of the medications you took today successfully treat your headache?”* is answered positively on the same day as the medication intake date.

4-Week Intervals

For Baseline and each 4-week period post-baseline in the trial, the number of MMDs will be derived as the number of migraine days within each 28-day interval using the imputation rules described below. The 4-week periods post-baseline that are considered are the following: Weeks 1-4, Weeks 5-8, Weeks 9-12, Weeks 13-16, Weeks 17-20 and Weeks 21-24.

In general, for 4-week periods where the number of reported eDiary days are at least 14 days out of the 28 days, prorating will be used to calculate the MMDs, and for 4-week periods where the number of reported eDiary days are less than 14 days out of the 28 days, the MMDs will be set to missing. Once prorating has been applied, a non-missing 4-week MMD value is considered a valid assessment.

Prorating

Intended to be used for 4-week periods where the eDiary is completed on at least 14 out of the 28 days, the prorating procedure consists of imputing days with missing information with the observed mean number of migraine days in the period as follows:

$$28^*(\text{Reported Migraine Days}/\text{Reported eDiary Days})$$

This imputation rule will also be used for the Baseline value regardless of the number of reported eDiary days in the screening period.

When the number of MMDs have been calculated for a given 4-week period, the result will be rounded to two decimals.

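### SAP 15.13.2 has no earliest day for counting a withdrawal questionnaire as Week 12, so forms from about Day 14 can enter the secondary ePRO analyses as observed Week 12 values

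*SAP*

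**What the plan says.** **Withdrawal questionnaires.** SAP 15.13.2 covers treated participants who withdraw before Week 12 and complete HIT-6, mMIDAS, MSQ, EQ-5D-5L, WPAI:M, HADS, TSQM-9, PGIC, MBS and HCRU at the Withdrawal Visit. It states: "These assessments will be assigned to nominal Visit 5". A planned Visit 5 value takes precedence. Failing that, the rule is "In case, no planned assessments are present at Visit 5 or Visit 7 visits, the observation closest to ADAY = 82", with no limit on how far away that observation may be.

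**Who attends.** SAP 2.1 gives the rule for anyone leaving early, which reads: "except for those who withdraw their consent or are lost to follow-up, will be asked to attend a Withdrawal Visit as soon as possible". Protocol 8.7 is wider. A participant who withdraws consent during a visit may complete it as a Withdrawal Visit. One who does so during a decentralized contact is asked whether they will attend one. In both cases data up to and including that visit are used.

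**Visit 5 and the infusion.** Under 15.13.2, "If exactly one observation exists for a specific visit label, this should be used". Where there are several Week 12 observations, pre-infusion ones are preferred, but "If no such observation exists, choose the one closest to ADAY = 82". SAP 15.13.1 keeps an SDS:H labelled Visit 5 at Visit 5 even when it was done after that visit's date.

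**Analysis.** SAP 11.5 uses the FAS. There, "health-related quality of life scores test between EPTI and PBO at Week 4, Week 12 will use the similar MMRM model"; PGIC and TSQM-9 are in the same group, and MBS at Week 12 has an ANCOVA. Under SAP Section 4 the FAS requires "at least one valid post-baseline 4-week assessment of MMDs in Weeks 1-12".

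**The concern.** A value labelled Week 12 should describe the participant at about Week 12. For someone who leaves early and attends a Withdrawal Visit, the rule enters the last available form as an observed Week 12 value, whatever day it was done. The MMRM then does not treat Week 12 as missing for that person. Someone who leaves before Week 4 can have a Week 12 value and no Week 4 value.

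The SAP handles comparable data differently. In SAP 15.13.3 (Table 11), unscheduled and withdrawal vital signs count as Visit 5 pre-dose only from Day 43. In SAP 15.1.1, when reported diary days are "less than 14 days out of the 28 days, the MMDs will be set to missing". The sensitivity analyses in SAP 11.3.4 and 11.4.4 cover primary and key secondary endpoints only, so none tests the ePRO rule.

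The second gap concerns the end of the blinded comparison. SAP 3.2 ends the Placebo-controlled Period when the Visit 5 infusion begins, and from then on every participant receives eptinezumab (Protocol 6.1). SAP 17.1 footnote g requires ePROs before that infusion, and Protocol 8.5 requires the same of SDS:H. The assignment rules nevertheless admit post-infusion forms to Week 12.

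At stake is the meaning of the Week 12 time point in the secondary ePRO comparisons and the exploratory SDS:H comparison.

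**Working it through.** The plan gives no figure for this point. The one figure borrowed below is the 270 per group in SAP Section 14, which reproduces: 2 × (1.960 + 0.842)² × 6.2² / 1.5² = 268.2, so 269 per group against the stated 270.

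**1. Earliest day.** Inputs: FAS entry needs one valid 4-week MMD value (Section 4); a valid value needs at least 14 reported days of 28 (15.1.1); the Withdrawal Visit is held as soon as possible (2.1; Protocol 8.7). With dosing on Day 0 and Days 1 to 14 all reported, a participant qualifies for the FAS from Day 14. Withdrawal ePROs may be completed up to 3 days before the visit, so a form could date from about Day 11. Day 14 is therefore an approximate floor inferred from other rules; 15.13.2 does not state it.

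**2. Distance from Week 12.**
- From nominal Day 84: 84 − 14 = 70 days.
- From the SAP's selection target, ADAY 82: 82 − 14 = 68 days.
- Share of the period elapsed: 14/84 = 17%.
- Under the vital-signs window the earliest admissible day would be 43, which is 84 − 43 = 41 days before Day 84.

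**3. What an early form describes.** mMIDAS has a 1-month recall (SAP 15.3), read here as 28 days. A form on day d covers d − 27 to d.
- Day 14 form: Days −13 to 14, so 14 of 28 days fall on or before the dosing day.
- On-schedule Day 84 form: Days 57 to 84. Overlap with the Day 14 form: none. The last form with no overlap is Day 56 (Day 54 if ADAY 82 is the reference).
- Other instruments differ. WPAI:M recalls 7 days, PGIC rates change since Baseline, and MBS rates change since screening. Recall therefore fixes no single cut for all ePROs.

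**4. Candidate cuts.** Vital signs are scheduled at Days 0 and 84 in this period; the midpoint is 42, which matches Table 11 starting Visit 5 at Day 43. ePROs are scheduled at Weeks 4 and 12: (28 + 84)/2 = 56.

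**5. Post-infusion forms.** Following 15.13.2 through:
- one Visit 5 form, done after infusion: used;
- several, at least one before infusion: the pre-infusion form nearest the infusion is used;
- several, all after infusion: the one closest to ADAY 82 is used.

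So a post-infusion ePRO is accepted whenever no pre-infusion form exists. For SDS:H, 15.13.1 accepts a late Visit 5 form without even that condition.

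**6. Effect size: illustration only.** The documents give no rate of attended Withdrawal Visits and no ePRO effect. Suppose a share w of an arm's Week 12 values is reassigned, each g SD less improved than that arm's Week 12 mean. If these participants would otherwise have matched completers, the difference shifts by wE·gE − wP·gP.
- 5% in both arms, gaps 0.5 and 0.3: 0.025 − 0.015 = 0.010 SD.
- 8% against 2%, same gaps: 0.040 − 0.006 = 0.034 SD; with the arms exchanged, −0.034 SD.
- Unadjusted standard error at 270 per arm: √(2/270) = 0.086 SD, so these are 0.12 and 0.40 standard errors.

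If the participants would instead have stayed at their early level, the current rule has no shift, and setting the value to missing has the opposite one for anyone with no other post-baseline value. Shares and gaps are invented, simple means replace the MMRM, and all reassigned values are counted, including late ones. The figures do not rank the two rules.

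**The case against.** The rule is prespecified, identical in both arms and was finalised before unblinding. It keeps data that were actually collected. All affected between-arm analyses lie outside the nine-step hierarchy in SAP 11.2. If withdrawn participants would have stayed where they were, the current rule is the less biased one. All of this stands, and it rules out calling the rule biased. It does not answer the labelling problem: a Day 14 form is not a Week 12 observation.

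It can also be said that withdrawals are already visible. SAP 6.1 and 6.2 give counts and reasons by treatment group, dated listings and Kaplan-Meier plots. That stands too. A reader might infer that early withdrawal goes unreported by arm, and the documents contradict this. What is missing is only a flag showing which ePRO values were reassigned, and from which day.

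No cut follows uniquely from the plan. That stands, so any cut is a choice to be stated.

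A post-infusion form is a protocol deviation, and a form completed shortly after a 30-minute infusion would still recall mostly the placebo-controlled period. This makes the second gap small, but neither 15.13.1 nor 15.13.2 limits how long after infusion a Visit 5-labelled form may be done.

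**Conclusion.** The point holds and is minor. SAP 15.13.2 allows an observed Week 12 label on forms up to about 70 days early, and 15.13.1 and 15.13.2 allow post-infusion forms into Week 12. The Day 14 figure assumes complete diary reporting from Day 1 and an attended Withdrawal Visit at that time. The recall arithmetic assumes a 28-day month.

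Three stronger readings are tempting, and the documents do not support them:
- **That Week 12 ePRO results are biased for or against eptinezumab.** The direction depends on the unobserved course of withdrawn participants and on withdrawal by arm. The documents give neither.
- **That the main result is affected.** The primary and key secondary endpoints are derived from the eDiary and do not pass through 15.13.
- **That participants who withdraw consent cannot contribute.** SAP 2.1 alone suggests this, but under Protocol 8.7 a completed Withdrawal Visit is used, so the affected group can include them.

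The same rule applies to Visit 7, where analyses are descriptive only.

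**What to change.** 1. Add an ePRO visit window to SAP 15.13.2, as 15.13.3 has for vital signs, with a prespecified cut between the Week 4 and Week 12 visits. Examples are their nominal midpoint, Day 56, or the SAP's own Day 43. Map earlier withdrawal values to Week 4 if that slot is empty; otherwise list them and leave Week 12 missing. MBS has no Week 4 analysis, so early MBS values are listed only.
2. Where a Visit 5 infusion was given, admit only pre-infusion ePRO and SDS:H values to Week 12.
3. Flag reassigned values by arm and day, alongside the withdrawal outputs already planned in 6.1 and 6.2, and keep the current rule as a sensitivity analysis.
4. State that completed Withdrawal Visits after consent withdrawal are included, in line with Protocol 8.7.

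If unblinding has taken place, keep the current rule for the main analysis and report the windowed version as a labelled post hoc sensitivity analysis.

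The cost is SAP wording and some visit-mapping code, a few more missing Week 12 ePRO values, and an MBS analysis that is complete-case for early withdrawals. Some mistiming remains: with the cut at Day 56, a Day 57 form still counts as Week 12, 27 days early.
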